This prospective, randomized, controlled, single-blind clinical study was planned at the Physical Medicine and Rehabilitation (PMR) Clinic of Bursa Yüksek İhtisas Training and Research Hospital. Ethical approval for the study was obtained from the local ethics committee (number 2011-KAEK-252022/10-02). The study included volunteer participants who were postmenopausal women from Türkiye aged 45-65 years, who presented to the PMR clinic as outpatients between November 2022 and November 2023. Participants were selected based on bone mineral density (BMD) T-scores between -1 and -2.5, measured by dual-energy X-ray absorptiometry (DXA), and were evaluated according to the exclusion criteria to ensure eligibility for inclusion in the study. Patients with conditions other than osteoporosis that could affect the concentrations of bone formation and resorption markers, such as vertebral compression fracture, a history of traumatic or nontraumatic fractures in the past year, thyroid hormone disorders, parathyroid hormone disorders, liver function disorders, kidney function disorders, chronic heart failure, a history of malignancy, a history of rheumatological diseases, corticosteroid use, immunosuppressive drug use, anticonvulsant and heparin use, and those who could not complete sessions due to mechanical pain exacerbated during aerobic exercise on a treadmill (such as knee and hip osteoarthritis, back pain, etc.) were excluded from the study. Participants were determined to be in menopause by their gynecology and obstetrics doctors. FSH and estrogen levels, which can be used in the diagnosis of menopause, were not evaluated. Participants were not taking antiresorptive or anabolic agent treatments used in the pharmacological treatment of osteoporosis or HRT, which can be used during menopause.

Fifty patients who met these criteria were included in the study. Each patient was informed about the purpose of the study, the application method, duration, potential problems, and side effects, and they signed a consent form. The patients included in the study were numbered and divided into two groups by simple randomization using the closed envelope method: aerobic exercise group (n=25) and control group (n=25). Three patients in the exercise group and two patients in the control group did not participate in the follow-up examination conducted in the 12th week, so the study included 45 patients (exercise, n=22; control, n=23) (Figure 1).

[figure not shown]

Figure 1

Treatment Protocol

All patients were prescribed 2000 IU of vitamin D (cholecalciferol) and 1200 mg of calcium carbonate daily for 12 weeks. The aerobic exercise program and assessments were conducted at the Exercise Room of Hospital. The exercise group participated in a supervised aerobic exercise program involving treadmill walking (model: Grand Power: 2.5 HP, DP2011017654) for 4 weeks, 3 days a week, for 30 minutes a day, at an intensity of 40-60% of the maximal heart rate. Additionally, they were shown an exercise program at the initial assessment that included balance, posture, and endurance exercises using body weight and weights to be performed 3 days a week, with 3 sets of 10 repetitions. The exercise program consisted of a 10-minute warm-up, 30 minutes of aerobic exercise, and a 10-minute cool-down. All participants completed the exercise program under supervision. Blood pressure, pulse, and oxygen saturation were measured with a pulse oximeter before and after each exercise session. The control group was not included in any exercise program. Patients in the exercise group continued outdoor walking, balance, posture, and resistance exercises for up to 12 weeks of follow-up between November 2022 and May 2023 and were followed up by phone once a week.

Statistical analysis

SPSS version 25 statistical software was used for data analysis. Descriptive findings for categorical variables are expressed as percentages, and continuous variables are presented as the mean \pm standard error and median, minimum, and maximum values. For binary analyses, the chi-square test was used for categorical variables, while the Mann–Whitney U test and the Wilcoxon signed-rank test were employed for continuous variables since they did not meet the normal distribution prerequisites.

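### Do the two stated calendar windows mean that the arms were not recruited and followed over the same period?

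*Combined protocol and SAP*

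**What the plan says.** Two places in the combined protocol and SAP give calendar dates.

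- **Opening section on design and participants.** Participants were women "who presented to the PMR clinic as outpatients between November 2022 and November 2023". They were "divided into two groups by simple randomization using the closed envelope method", 25 to each arm. Three exercise patients and two controls "did not participate in the follow-up examination conducted in the 12th week", which leaves 22 and 23.
- **Treatment Protocol.** Supervised treadmill walking ran "for 4 weeks, 3 days a week, for 30 minutes a day". After that, "Patients in the exercise group continued outdoor walking, balance, posture, and resistance exercises". The stated period for this phase is "for up to 12 weeks of follow-up between November 2022 and May 2023", with a weekly telephone call. All patients were prescribed "2000 IU of vitamin D (cholecalciferol) and 1200 mg of calcium carbonate daily for 12 weeks". No calendar dates are given for the control arm.

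The Statistical analysis section names chi-square, Mann–Whitney and Wilcoxon signed-rank tests. None of them uses entry date.

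**The concern.** The first window is about 13 months long and the second about 7, and both open in November 2022. If patients really entered through November 2023 and every exercise patient was followed inside the shorter window, patients who entered late could only have been controls. Those controls would have no exercise patients from the same months beside them. The programme includes outdoor walking and all patients take vitamin D, so time of year could plausibly bear on the results. The treatment contrast would then be partly a contrast between calendar periods, and the planned two-group tests could not separate the two. Even without that, a reader cannot tell from the text when patients were randomised and examined.

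**Working it through.** **Inputs.** Presentation window November 2022 to November 2023, week-12 examination and 25:25 allocation (opening section); exercise follow-up window November 2022 to May 2023, up to 12 weeks, and 4 supervised weeks (Treatment Protocol). The document gives months only, so the last day of the month is used as the most lenient reading.

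**Step 1: latest start compatible with the exercise window.**
- 12 weeks in total: 31 May 2023 − 84 days = 8 March 2023.
- 12 weeks after the 4 supervised weeks: 31 May 2023 − 112 days = 8 February 2023.
- Follow-up shorter than 12 weeks, which the wording allows, permits a later start, but nobody entering from 1 June 2023 could have any exercise follow-up inside the window.

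**Step 2: the end of the presentation window.**
- A patient presenting on 30 November 2023 reaches week 12 on 30 November 2023 + 84 days = 22 February 2024.
- If November 2023 is instead the end of the whole study, the last start is 30 November 2023 − 84 days = 7 September 2023, still well after 8 March. Moving the meaning of that date does not by itself close the gap.

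**Step 3: what could be true.**

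| Reading | What happened | Effect on the comparison |
|---|---|---|
| 1 | May 2023 is misstated | None; a date is wrong |
| 2 | November 2023 is misstated or a loose outer bound, and everyone entered early | None; both windows can stand if it is a loose bound |
| 3 | Some patients entered late and all were controls | Exercise partly mixed with calendar period |

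**Step 4: how reading 3 fits the stated allocation.** Let k be the number of the 50 who entered too late for the exercise window. The document does not give k, and it may be zero. With 25 of 50 allocated at random to control, P(all k are controls) = C(25,k)/C(50,k).
- k = 1: 25/50 = 0.50
- k = 3: (25 × 24 × 23)/(50 × 49 × 48) = 13,800/117,600 = 0.117
- k = 5: 0.025
- k = 10: 0.0003

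Tossing a fair coin for each patient gives much the same: 0.5^k = 0.50, 0.125, 0.031 and 0.001.

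One or two late controls could arise by chance. They would be 1/23 = 4% to 2/23 = 9% of the controls analysed, if they completed. They would also be a chance imbalance in entry date under valid randomisation, which does not bias the comparison. A large block of late controls would require that allocation was not carried out as described.

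**Step 5: counts.** 25 − 3 = 22, 25 − 2 = 23 and 22 + 23 = 45, as stated. No count depends on either window.

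**The case for a change.** The strongest case for acting is that entry and follow-up dates are basic facts of a randomised trial, that the mismatch survives every obvious re-reading of the wording, and that dates are given for one arm only. On the widest reading of the months, starts compatible with 12 weeks of exercise follow-up (1 November 2022 to 8 March 2023) cover 128 of the 395 days of the presentation window, or 32%. Checking the log costs almost nothing, and it would show whether the arms were concurrent.

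Most of this is right as far as it goes. The discrepancy is real, and the visible text does not say which date is off. But the 32% counts calendar days, not patients. The document gives no accrual rate, and 50 outpatients could all have entered in the first few months. The seasonal argument needs reading 3 to be true and also needs a seasonal effect whose size the document does not give. Supplementation, being common to both arms, is no evidence of a difference between them. What stands is a request for clear dates in the report.

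A change to the analysis, such as restricting the comparison to early controls, does not follow. It would discard randomised patients to repair a fault that nobody has shown, and it would cost precision.

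**Conclusion.** The two windows are not reconciled, but no change to the plan follows. They date different things, presentation at the clinic and exercise follow-up, and both can hold if every exercise patient with a full 12 weeks started by 8 March 2023 (8 February if the supervised weeks come first). Under the two simpler readings the effect on the results is nil. The harmful reading has no direct support and sits badly with simple randomisation from one pool: a 12% chance for three late entrants and 0.03% for ten. No sample size, test or count depends on either window.

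This rests on two assumptions: that allocation was carried out as the opening section describes, and that the flow diagram, which is not visible here, does not show otherwise. The ordinary reporting of first and last enrolment and last week-12 visit for each arm, taken from the existing log, settles which date is loose and confirms that the arms ran together.

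### Continuous outcomes rest on unadjusted Mann–Whitney and Wilcoxon tests, with no stated input, no lead test and no baseline-adjusted comparison between arms

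*Combined protocol and SAP*

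**What the plan says.** The Statistical analysis section covers continuous outcomes in one clause: "the Mann–Whitney U test and the Wilcoxon signed-rank test were employed for continuous variables", with the reason given as "since they did not meet the normal distribution prerequisites". The summaries it lists for continuous variables are the mean with its "standard error and median, minimum, and maximum values". These describe each group; no difference between arms and no confidence interval is named. Chi-square is reserved for categorical variables and plays no part here.

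Two other places bear on the point. The opening study description gives 25 patients randomised to each arm, with 22 (exercise) and 23 (control) analysed after losses at week 12. The Treatment Protocol section says: "All patients were prescribed 2000 IU of vitamin D (cholecalciferol) and 1200 mg of calcium carbonate daily for 12 weeks". Both arms therefore start something at baseline that could move the outcomes.

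The text does not say what the Wilcoxon test compares. Signed-rank is a paired test, and the Treatment Protocol mentions an initial assessment, so the natural reading is before versus after within each arm. Baseline values are then available.

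**The concern.** Three things are left open.

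- **Input to Mann–Whitney.** It could be applied to week-12 values or to changes from baseline. These are different analyses with different power, and they can disagree on the same data.
- **Which test carries the conclusion.** Only a between-arm test uses the randomised comparison. A before–after change in the exercise arm mixes exercise with supplements, regression to the mean and time. If the two within-arm results are read side by side, significant with exercise and not in control, the trial could claim an exercise effect that is not there.
- **Use of baseline.** With about 22 patients per arm, precision is scarce. Baseline values are implied to exist, yet no named between-arm analysis adjusts for them.

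**Working it through.** **Inputs.** From the documents: 25 − 3 = 22 exercise, 25 − 2 = 23 control, 45 in total. The documents give no alpha, effect size, SD or correlation, and no power figure to reproduce. Assumed: two-sided 0.05, a true between-arm effect of 0.6 SD, and a baseline-to-week-12 correlation ρ from 0.3 to 0.8.

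**Step 1: formula check.** Relative to the outcome variance, the variance factor f is 1 for week-12 values, 2(1 − ρ) for changes and 1 − ρ² after baseline adjustment. The standard error in SD units is √f × √(1/22 + 1/23) = √f × 0.298, and power ≈ Φ(0.6/SE − 1.96).

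| ρ | f: week-12 / change / adjusted | Power: week-12 / change / adjusted |
|---|---|---|
| 0.3 | 1 / 1.40 / 0.91 | 52% / 40% / 56% |
| 0.5 | 1 / 1.00 / 0.75 | 52% / 52% / 64% |
| 0.7 | 1 / 0.60 / 0.51 | 52% / 74% / 80% |
| 0.8 | 1 / 0.40 / 0.36 | 52% / 89% / 92% |

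Changes lose to week-12 values below ρ = 0.5 and beat them above it. At ρ = 0.5, adjustment is worth as much as raising the total from 45 to 45/0.75 = 60 patients.

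**Step 2: simulation with skewed data.** The plan reports non-normality, so the actual tests were simulated on a log-normal outcome with a 0.6 SD shift on the log scale (5,000 runs per row). Power in %:

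| ρ | Mann–Whitney, week 12 | Mann–Whitney, change | Quade rank ANCOVA | Log-scale ANCOVA |
|---|---|---|---|---|
| 0.3 | 46.3 | 37.6 | 49.8 | 52.3 |
| 0.5 | 46.9 | 48.1 | 56.6 | 60.0 |
| 0.7 | 48.4 | 68.8 | 72.5 | 77.1 |
| 0.8 | 48.5 | 85.7 | 85.8 | 90.8 |

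Quade minus week-12 values: 3.5 / 9.7 / 24.1 / 37.3 points. Quade minus changes: 12.2 / 8.5 / 3.7 / 0.1 points. Type I error was 4.2–5.5% for all four tests.

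**Step 3: a case where the log scale is not right by construction.** With gamma-shaped outcomes (shape 2, offset 1), an additive 0.6 SD shift and 2,500 runs, power in the same column order was:

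- ρ 0.3: 64.4 / 44.8 / 67.4 / 72.3%
- ρ 0.5: 61.8 / 55.8 / 72.6 / 78.0%
- ρ 0.7: 63.9 / 76.2 / 85.4 / 90.4%
- ρ 0.8: 63.7 / 91.0 / 93.6 / 96.5%

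Type I error was 4.0–5.4%.

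**Step 4: cost of an open choice.** With normal data and 10,000 runs, the two Mann–Whitney versions reached different verdicts in 32%, 35% and 40% of trials at ρ = 0.3, 0.5 and 0.7 under a 0.6 SD effect. With no effect, each rejects about 5% of the time, but at least one does so in about 9%. Choosing the input after seeing results could nearly double the false-positive rate.

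**Step 5: within-arm tests when exercise does nothing.** If both arms truly change by the same amount and each signed-rank test is significant with probability p, exactly one is significant with probability 2p(1 − p), and exercise alone with p(1 − p). These peak at 50% and 25% when p = 0.5. Simulated values (log-normal, 4,000 runs):

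| Equal change | Exactly one arm (exercise only), ρ = 0.5 | Exactly one arm (exercise only), ρ = 0.7 |
|---|---|---|
| 0.3 SD | 37.6% (19.4%) | 47.2% (22.8%) |
| 0.4 SD | 46.9% (22.8%) | 49.0% (23.4%) |
| 0.5 SD | 48.9% (24.0%) | 34.3% (16.7%) |

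In the same runs the between-arm Quade test was significant in 4.5–5.5%. Over changes of 0.2–0.6 SD and ρ of 0.3–0.8, the two ranges widen to 5–50% and 2–25%.

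**The case against.** The best defence is that the conventional reading is harmless: Mann–Whitney compares the arms, Wilcoxon describes change within each, and nothing says that conclusions come from the latter. On that reading the between-arm test is valid, and preferring an adjusted test is a matter of efficiency. The gain also depends on quantities the documents do not give. If changes were analysed and ρ is 0.7–0.8, Quade adds 4 points or none; one further check at ρ = 0.8 with mild skew put changes slightly ahead (87% against 85%). The study also appears complete, so an adjusted analysis may no longer count as prespecified.

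Much of this is fair. Misuse of the within-arm tests is a risk, not something shown, and the large power gains need both week-12 values as input and a high correlation. But the defence assumes an input and a hierarchy that the text does not state. Quade's method needs no guess about ρ: it was about as good as or better than both Mann–Whitney versions across the range. Non-normality is no obstacle to a rank-based adjustment.

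One qualification stands. Five of 50 randomised patients are not analysed, so validity among the 45 also needs an assumption about the missing data. That is a separate matter, and baseline adjustment does not by itself resolve it.

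**Conclusion.** The concern holds. The analysis of continuous outcomes is underspecified and leaves out an inexpensive gain in precision. The existing between-arm test is not invalid. Under the log-normal assumptions, Quade's rank ANCOVA gains about 4 to 37 points of power over week-12 values and 12 to 0 points over changes as ρ rises from 0.3 to 0.8.

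The false-claim risk is conditional on side-by-side reading of the within-arm tests. With equal changes of 0.3–0.5 SD and ρ of 0.5–0.7, that reading would favour exercise alone in 17–24% of trials with no exercise effect. All these figures rest on the assumed effect, correlation, distribution and 5% level. The gaps in the text do not.

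**What to change.** - State whether Mann–Whitney compares week-12 values or changes.
- Make one between-arm comparison at week 12, adjusted for the same variable's baseline, the sole basis for conclusions about exercise. Use Quade's rank ANCOVA as the test: rank outcome and baseline, regress one on the other, and compare residuals between arms. This keeps the non-parametric approach.
- Where a log scale fits the outcome, add ANCOVA on that scale for an estimate and 95% confidence interval. Where it does not, a Hodges–Lehmann shift with its interval can accompany the Mann–Whitney result, labelled unadjusted.
- Report the within-arm Wilcoxon results as description only.
- If the data have already been analysed, label the adjusted analysis post hoc and show it beside the original tests. The section is written in the past tense and normality has already been judged on the data, so this is likely to apply.

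The cost is one model per outcome in the same software and one degree of freedom, with no new data or patients.

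### The statistical analysis names no deciding comparison, significance level or multiplicity rule, so a conclusion about exercise could rest on any of several tests, including within-arm ones

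*Combined protocol and SAP*

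**What the plan says.** The Statistical analysis section names the software, the descriptive statistics and three tests. For continuous variables it names the Mann–Whitney test, and with it "the Wilcoxon signed-rank test were employed for continuous variables since they did not meet the normal distribution prerequisites". For categorical variables, "the chi-square test was used for categorical variables". The section ends there. It does not say which variables are outcomes, which test decides efficacy, what significance level applies, whether tests are two-sided, or how multiple tests are handled.

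The available text has no outcome list. The nearest indication of what was measured is in the exclusion criteria of the opening study description, which rule out conditions that "could affect the concentrations of bone formation and resorption markers".

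The same description gives 25 randomized to each arm and 22 exercise and 23 control patients after losses at the week-12 examination. The Treatment Protocol section prescribes vitamin D and calcium to all patients for 12 weeks, and exercise to one arm only.

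**The concern.** Mann–Whitney compares independent groups and Wilcoxon signed-rank compares paired values. In a two-arm trial with one follow-up examination, the natural use of the pair is a between-arm test plus a before-after test in each arm, which makes up to three tests per outcome. With no deciding test and no adjustment, a positive conclusion could rest on whichever test came out most favourably, and the overall error rate would then not be controlled.

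The within-arm tests raise a second problem that does not depend on counting. Because supplements went to both arms, a significant before-after change in the exercise arm does not separate exercise from supplementation, passage of time or regression to the mean. Only a comparison between the arms does. The plan does not say that the between-arm comparison carries the conclusion.

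**Working it through.** The plan states no error rate, power or sample-size calculation, so there is no figure of its own to reproduce. The check asks how large the familywise error (the chance of at least one p < 0.05 when nothing is going on) could be.

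**Inputs from the document**
- 22 exercise and 23 control patients with week-12 data (opening study description).
- Mann–Whitney and Wilcoxon signed-rank for continuous variables (Statistical analysis).

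**Assumptions, because the document is silent**
- Two-sided 0.05 per test.
- Number of continuous outcomes, K: 1, 2 or 4.
- One between-arm and two within-arm tests per outcome where both kinds are counted.
- Normally distributed data. This is a convenience; the Mann–Whitney null rate does not depend on the shape.

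**Step 1: independent tests.** Familywise error = 1 − 0.95^m for m tests.
- Between-arm only, K = 2: 1 − 0.95² = 9.75%.
- Between-arm only, K = 4: 1 − 0.95⁴ = 18.5%.
- All three tests, K = 1 (m = 3): 1 − 0.95³ = 14.3%.
- All three tests, K = 2 (m = 6): 1 − 0.95⁶ = 26.5%.

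**Step 2: simulation at 22 v 23.** Outcomes may be correlated, and the between-arm and within-arm tests share data, so the independent formula is only a guide. Two set-ups were used, both with no arm difference and no change in either arm:
- (a) Mann–Whitney on change scores, correlation between outcomes 0 to 0.8.
- (b) Mann–Whitney on week-12 values, baseline-to-week-12 correlation 0.6, correlation between outcomes 0.3. A repeat at other outcome correlations gave similar results.

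| Outcomes | Between-arm tests only | Between-arm and within-arm tests |
|---|---|---|
| 1 | about 5% (4.7% in a, 4.9% in b) | 11.4% (a), 13.1% (b) |
| 2 | 8–10% | 18–22% (a), 24–26% (b) |
| 4 | about 16% (b) | about 41% (b) |

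**Step 3: what the columns mean.** The right-hand column requires that neither arm changes from baseline. With supplements in both arms that may be false. A significant Wilcoxon result may then be a true change rather than a false positive, so the column does not measure error in that case. It would still not be evidence for exercise, since the control arm would be expected to change for the same reason. The left-hand column does not depend on this assumption; it needs only that the arms do not differ.

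**Step 4: after correction.** One pre-specified between-arm test gives about 5% (4.7% simulated). Holm holds the familywise rate at or below 5%. Its strictest step compares the smallest p-value with 0.05/2 = 0.025 for two outcomes and 0.05/4 = 0.0125 for four.

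**The case against.** The strongest reply is that much of the inflation is assumed. Several points in it stand.

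- A reader might infer that every continuous outcome was tested both between and within arms. The section says only that the two tests were used for continuous variables. It does not mention within-arm testing or say that each variable received both tests, and continuous variables include baseline descriptors such as age. The three-tests-per-outcome count is the natural reading, not a stated fact.
- A reader might infer at least two marker outcomes. The plural appears only inside an exclusion criterion, which suggests what was measured but does not fix how many outcomes were tested. The four-outcome figures are illustrative.
- A reader might conclude that the trial has no primary outcome. Part of the front of the document was not available, and an objective or primary outcome could be stated there. The absence holds only for the text that could be read. The gaps in significance level, deciding comparison and adjustment are firmer, because the Statistical analysis section is present.
- A reader might state that the error rate is well above 5%. For between-arm tests with one outcome it is not. The larger figures need either several outcomes or within-arm tests under a no-change null that the supplements make doubtful.
- Nothing in the document says that a within-arm p-value would be presented as an exercise effect. The problem is that nothing prevents it.
- The text is in the past tense and the patients have been followed, so a primary outcome chosen now would be post hoc.

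These points limit the size of the problem and shape the remedy. They do not supply the missing rule: an outcome list elsewhere would not by itself say which comparison decides, at what level, or how several outcomes are handled.

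**Conclusion.** The concern holds in a limited form. The Statistical analysis section leaves the deciding comparison, significance level and multiplicity handling unstated, and the available text names no primary outcome.

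The relevant figures are the between-arm ones: about 5% for one outcome, 8–10% for two and about 16% for four, assuming two-sided 0.05 and an outcome count that the plan does not give. Counting within-arm tests raises the figure to about 11–13% for one outcome and 18–26% for two, on the further assumptions that both arms are tested and neither changes. No single error rate can be attributed to this trial.

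The part that needs no assumed outcome count is the interpretation: because supplements were prescribed to everyone, a before-after result in the exercise arm cannot show an effect of exercise. This is a cheap improvement to the analysis and its reporting. It does not show that any conclusion is false.

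**What to change.** 1. Base any conclusion about exercise only on between-arm comparisons of week-12 values adjusted for baseline, at two-sided 0.05. Given the stated non-normality, a rank-based ANCOVA is one suitable method.
2. Treat an outcome as primary only if it was documented as such before the data were seen, and cite that document. If there is none, do not choose one now; apply Holm across all between-arm outcomes.
3. Where a documented primary exists, adjust the remaining between-arm outcomes by Holm or label them exploratory.
4. Report how many outcomes and how many tests were run.
5. Present within-arm Wilcoxon results as descriptive, not as evidence of an exercise effect.

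The cost is revised wording and a re-run of the between-arm analysis on data already collected, with no further patients or procedures. The downside is a stricter threshold for the outcomes adjusted by Holm, which lowers power in a trial of 45 analysed patients.
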